## Synopsis

### Purpose

This is a pilot study that will lead to a pragmatic clinical trial. It will evaluate the implementation of an embedded pragmatic, clinical intervention. The intervention will assess older adults (age 65+) in the Emergency Department (ED) for delirium and risk for undiagnosed cognitive impairment and dementia (UCID), refer patients who are found to be at risk for UCID for outpatient evaluation and primary care follow-up.

### Objectives

The primary objective of this pilot project is to evaluate the feasibility of incorporating and implementing a delirium and dementia assessment and referral protocol to assess for UCID in ED patients age 65 and older. This will lead to a future multicenter, pragmatic clinical trial.

The secondary objective is to determine optimal workflow for integration of cognitive impairment screening, referral assessment, and cognitive health follow-up in a pilot sample of patients and to analyze rates of screening, referral, and diagnosis of cognitive impairment or dementia.

### Study Population

All community dwelling ED patients 65 years of age or older seen in the Yale New Haven Health System (YNHHS) St. Raphael's Campus (SRC) ED or Northwestern Memorial Hospital (NMH) ED.

### Number of Participants

A total of 100 subjects (50 from each site) will be included to gather retrospective observational data via telephone follow-up and chart review. These data will provide estimates in rates of screening and referral for a pilot sample of ED patients to ascertain the feasibility. Additionally, we will compare differences in processes, utilization, and outcome endpoints across the two sites. The number of subjects will provide the needed information to inform a future pragmatic clinical trial proposal.

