#### **5.2 Number of Participants**

All patients 65+ years in age seen in both EDs during the study period will be screened in the ED using clinical screening for UCID.

A convenience sample of 100 hundred subjects (50 from each site) will be included for retrospective and prospective observational data via chart review and interview to evaluate rate of UCID detection in the ED, rates of referral for outpatient evaluation, rates of confirmed cognitive impairment or dementia by the outpatient evaluation, and differences across the two sites with processes, utilization, and outcome endpoints.

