## **6 Study Methods/Procedures**

### **6.1 Study Procedures**

#### **Clinical ED Practice Intervention.**

As part of routine ED care, clinicians conduct delirium screening at bedside to evaluate presence of cognitive impairment in ED who are 65 years and older. The intervention will augment this process to include questions assessing for documented history of dementia or asking the patient, or caregivers present, in the ED if the patient has had any memory or thinking problems in the past year. If clinicians suspect the patient may have cognitive impairment, regardless of the response from patient or caregiver, and the patient has no documented history of dementia, the physicians may refer these patients to available outpatient cognitive evaluation. Referral will occur using EMR outpatient consult requests or by emailing outpatient clinics for available appointments as part of routine patient care referral processes.

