#### **6.1.1 Data Collection**

As this is a pilot study, we will gather a convenience sample of 100 participants who are eligible to be referred for outpatient cognitive assessment (50 from each site) will be evaluated. Data will be collected by telephone interview follow-up and chart review for observational characterize subjects, sites, processes, utilization, and outcome endpoints.

Research staff at both sites will contact by telephone the selected participants to conduct two focused interviews at 1-6 weeks and 3 months post-ED visit. The survey will assess the participants experiences through the process, findings of the assessment and the participants follow-up care plan. A retrospective chart review will be conducted on these participants. Trained research staff at each site will conduct chart review in the Electronic Medical Record to determine rates of:

- Healthcare utilization by the patients during the subsequent 30 days in addition to the requested outpatient cognitive assessment, inpatient hospitalizations, and/or ED revisits up to 6 months prior to the current ED visit

- Referral and completion of outpatient cognitive assessment
- New outpatient diagnoses of Alzheimer's Diseases or Related Dementia diagnoses or mild cognitive impairment
- Documentation of Outpatient Cognitive Assessment communication with the patients' primary care providers or other consults of results and recommendations for brain health treatment and management.

Trained research assistants will review the medical records of potentially eligible participants seen in the ED during the study period to assess clinician compliance and acceptance of screening intervention.

Data for this study will be collected, recorded and stored using Redcap (Research Electronic Data Capture). Redcap is a secure, web application designed to support data capture for research studies. Data from any paper study forms will be entered into Redcap and then stored in locked file cabinets restricted to the study team. Data coordination, data management, and database design will occur within the Yale School of Medicine's Program on Aging. See Table 1 for data points that will be collected.

Retrospective chart review will be conducted on a subset of 100 patients as part of study enrollment: We will collect data on a subset of patients meeting inclusion criteria (50 from each site, for a total of 100 subjects).

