### **7 Statistical Design**

This is an observational pilot study and descriptive statistics will be completed comparing demographic and clinical characteristics of all patients 65+ discharged from the ED (denominator) versus those referred from the ED for outpatient cognitive impairment assessment. Student's t-test will be used for continuous variables (if normally distributed (e.g. age)) or the Wilcoxon rank-sum test (if not normally distributed (e.g., length of stay)), and the Chi-square test or Fisher's exact test for binary/categorical variables. All tests will be 2-sided at a significance level of 5%.

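### The group comparisons in Sections 7 and 7.3 do not adjust for site, so a difference between the two hospitals can appear as a difference between patient groups

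*Combined protocol and SAP*

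**What the plan says.** Enrolment is a convenience sample with a fixed quota per hospital: "A total of 100 subjects (50 from each site) will be included" (Synopsis, Number of Participants; repeated in Sections 5.2 and 6.1.1).

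Section 7 compares "all patients 65+ discharged from the ED (denominator) versus those referred from the ED for outpatient cognitive impairment assessment". The tests are the t-test or Wilcoxon rank-sum test for continuous variables and the "Chi-square test or Fisher's exact test for binary/categorical variables", all two-sided at 5%. No site term, stratum or weight is mentioned.

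A second comparison appears in two places. Section 5.5 seeks a waiver for the records of all older ED patients so that they can be set against the enrolled group. Section 7.3 describes the overall eligible patients at both sites alongside the subset of 100.

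The plan does not ignore site. The Synopsis says "we will compare differences in processes, utilization, and outcome endpoints across the two sites", and Section 5.2 repeats the aim. Neither place gives a method.

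Section 4.2.1 defines the primary screening and detection rates on all older ED patients, not only on the 100.

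**The concern.** Two hospitals contribute to every comparison, and the named tests treat their patients as one group. That is harmless only if the sites are alike in the respects that matter. There are two separate mechanisms.

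- **Referred versus all discharged (Section 7).** If one site refers a larger share of its patients, it is over-represented among the referred. Any trait more common at that site then looks associated with referral, even if referral is unrelated to the trait within each hospital. Referral is at the physician's discretion and depends on available outpatient evaluation (Section 6.1), so equal referral rates cannot be presumed.
- **Enrolled versus all eligible (Sections 5.5 and 7.3).** The enrolled group is half from each site by design, while the eligible population carries the sites' natural volumes. If those volumes are unequal, the quota itself creates a site imbalance between the groups.

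A related point concerns rates taken from the 100, such as completion of the outpatient evaluation and diagnosis. A crude combined figure is an equal-weight average of the two sites, whatever their volumes.

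Sections 4.2 and 7.1 say the results will inform effect sizes and sample-size calculations for the later trial. A misread predictor of referral, or a rate with unintended weights, would carry into that design.

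**Working it through.** The plan gives no power, precision, site volume or rate, so it has no figure to reproduce beyond 50 + 50 = 100. All volumes, prevalences and rates below are assumptions for illustration.

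**1. Referred versus all discharged**

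Notation: w = site A's share of discharges; r = referral rate; x = trait prevalence. Within each site the trait is unrelated to referral.

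- Site A's share of the referred: s = w·rA / [w·rA + (1−w)·rB]
- Trait among referred: s·xA + (1−s)·xB
- Trait among all discharged: w·xA + (1−w)·xB

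Assume 10,000 discharges per site, xA = 30%, xB = 10%.

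- Referral 10% and 2%: 1,000 and 200 referred. Trait among referred = (300 + 20)/1,200 = 26.7%. Among all discharged = (3,000 + 1,000)/20,000 = 20.0%. Gap 6.7 points. Against the non-referred it is (2,700 + 980)/18,800 = 19.6%, a gap of 7.1 points.
- Referral 6% and 3%: (180 + 30)/900 = 23.3% against 20.0%. Gap 3.3 points.
- The direction can reverse. With equal volumes, referral 2% and 6%, and prevalences 40% and 20%, s = 0.25. The referred figure is 0.25 × 40% + 0.75 × 20% = 25%, against 30% overall.

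**2. Enrolled versus all eligible**

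The enrolled prevalence is (xA + xB)/2 and the eligible prevalence is w·xA + (1−w)·xB, where w is now site A's share of eligible patients. The expected difference is (0.5 − w)(xA − xB). With 40% and 20%, it is −4 points at w = 0.7 (30% against 34%) and −6 points at w = 0.8 (30% against 36%).

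The simulation used 4,000 runs per setting. It compared 100 enrolled (50 per site) with the remaining 4,900 of 5,000 eligible, with no within-site difference. Rejection rates at 5% for the unstratified chi-square and the site-stratified Cochran-Mantel-Haenszel test were:

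| Site A share of eligible | Prevalence 40% / 20%: unstratified, stratified | Prevalence 60% / 20%: unstratified, stratified |
|---|---|---|
| 50% | 4.5%, 5.0% | 3.4%, 5.3% |
| 60% | 6.7%, 4.5% | 10.8%, 5.1% |
| 70% | 12.1%, 4.4% | 35.6%, 5.2% |
| 80% | 22.2%, 4.6% | 68.8%, 5.6% |

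With 30% at both sites, both tests stay near 5% whatever the volumes.

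**3. Combined rates from the 100**

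- Assumed completion of 60% and 30% with 5:1 referral volumes: weighted, (5/6) × 60% + (1/6) × 30% = 55%; crude 50/50, (60% + 30%)/2 = 45%.
- With the same rates and 50% to 80% of patients at site A, the gap runs from 0 to 9 points.
- For scale, the Wilson 95% interval at 30% is 21.9% to 39.6% for n = 100 and 19.1% to 43.8% for n = 50.
- Precision cost of weighting at 5:1, assuming similar variances by site: effective n = 50 / [(5/6)² + (1/6)²] = 50 / (26/36) ≈ 69.

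**The case against.** The strongest reply is that this is a feasibility pilot with descriptive aims. Section 4.2 says no hypotheses are tested, and a marginal description of who was referred, site mix included, is a legitimate target. The plan also intends to compare the sites, and equal enrolment suits that purpose. The magnitudes rest on chosen inputs and vanish if the sites are alike. The weighting gap is mostly smaller than the sampling error.

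Much of this stands, and it limits the point. But Section 7 does set tests at 5%, and a descriptive contrast is distorted by site mix just as a test is. Comparing endpoints between sites does not adjust the referred-versus-discharged or enrolled-versus-eligible contrasts. Sampling error is shown by an interval; a weighting shift is not.

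A reader might infer four stronger readings that the documents do not support:

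- **That the plan states it will pool the sites.** It does not. Pooling is inferred from silence, although the named tests default to it.
- **That the 50/50 quota drives the Section 7 gap.** That comparison is not tied to the 100; unequal referral rates drive it. The quota matters for the enrolled-versus-eligible comparison, for crude rates from the 100, or if the referred group were taken to mean the 100.
- **That two referral routes show a site difference.** Section 6.1 says only "Referral will occur using EMR outpatient consult requests or by emailing outpatient clinics for available appointments" and does not assign a route to a hospital.
- **That the primary rates carry arbitrary weights.** Section 4.2.1 defines them on all older ED patients, so they carry natural volumes.

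**Conclusion.** The point holds in limited form. As written, Sections 7 and 7.3 allow a site difference to be read as a group difference, because no comparison of patient groups is stratified or adjusted for site. This requires patient mix to differ by site, together with referral rates (first comparison) or eligible volumes (second comparison).

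The documents do not allow the size to be known. In the assumed cases it is a spurious gap of about 3 to 7 points in the first comparison. In the second, the false-positive rate is about 12% to 22% at prevalences of 40% and 20% with 70% to 80% of eligible patients at one site. Larger prevalence differences make it worse; identical sites remove it. The weighting issue is confined to combined rates from the 100. For a feasibility pilot this is a modest analytic gap, worth closing because the remedy is cheap and the results feed the next trial.

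**What to change.** - **Sections 7 and 7.3:** show both comparisons by site. Replace the unstratified tests with site-stratified ones: Cochran-Mantel-Haenszel for categorical variables, and the van Elteren test or regression with a site term for continuous ones.
- **Rates from the 100:** report completion and diagnosis by site as the main result. If a combined rate is given, state that the crude figure is an equal-weight site average. Add a version weighted by each site's number of patients in the population that rate describes, for example referred patients for completion, and state the weights. The screening log in Section 8.4, which tracks referred patients, could supply those counts.
- **Planned between-site comparison:** name its method.
- **Rates on all older ED patients (Section 4.2.1):** no reweighting is needed.

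Enrolment and the equal quota stay as they are. The cost is slightly more analysis and a wider interval for any weighted rate (effective n about 69 rather than 100 at an assumed 5:1 volume ratio). Weighting corrects the site mix only; it cannot make a convenience sample representative.

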### Study Design

The study is observational consisting of telephone interviews and medical record review.

### Study Duration

The study period is January 2021 – December 2022. Subject participation will take place over approximately 3 months and will occur January 2021 - December 2021.

### Outcome Variables

Primary outcome: ED screening and detection rates of delirium, vs. suspect dementia, vs. no cognitive deficits.

**Secondary outcomes:**

- Rate of screened patients who are referred to outpatient cognitive evaluation
- Rate of screened patients who have outpatient cognitive evaluation
- Rate of screened patients with outpatient evaluation that test positive for dementia

For patients identified as at risk for dementia:

- Referral for additional services
- Rate of primary care follow-up referral
- Rate of cognitive brain health plan, including changes in medications
- New diagnosis of Alzheimer's Disease and Related Dementias

## Abbreviations

Abbreviation	Explanation
AEs	Adverse events
ED	Emergency Department
MCI	Mild Cognitive Impairment
NIA	National Institute of Aging
NMH	Northwestern Memorial Hospital
Redcap	Research Electronic Data Capture
UCID	Undiagnosed Cognitive Impairment and Dementia
YNHH	Yale New Haven Hospital

### Protocol Revision History

Version Date	Summary of Substantial Changes
12/11/2020	IRB submission
6/28/2021	Update protocol to allow for calling potential participants in 1-6 weeks post-ED visit

## **1 Background**

### **1.1 Background**

Many older adults live with unrecognized cognitive impairment and dementia (UCID). Cognitive impairment, which increases with age and multimorbidity, often goes undetected and persons may not even realize they have impairment. These persons may be at greatest risk of poor health outcomes. Detecting UCID in the ED has important public health implications, as it can guide treatment and improve health outcomes for affected persons. Identification of patients who may have dementia in the ED would expedite diagnosis and effective management, identify essential patient and caregiver resources, and likely improve safety outcomes. UCID may be a cause of increased ED use as it has been shown that patients with dementia diagnoses have a higher rates of ED visits and return ED visits within 30-days of discharge. Though assessment for dementia is not traditionally performed in the ED, many patients in the ED are at high risk for it and detection at this point of contact may provide a pathway for improved care delivery and outcomes.

## **2 Rationale/Significance**

### **2.1 Rationale and Study Significance**

Limitations in standard emergency care and the ED environment can make detection of patients UCID complex. Emergency clinicians must deal with acute and urgent medical issues including delirium which can be difficult to differentiate or may co-occur with cognitive impairment for persons living with dementia. Identifying patients with UCID in the ED will impact clinical decision making, patient care, and patient outcomes. Before such programs can come into existence, however, it needs to be determined if integrating cognitive assessments in the ED (by incorporating into clinical care with training and electronic screening tools) is feasible. Implementation will require changes to workflow, determining the rates of ED screening of patients presenting with UCID, and rates of referral of patients and families for additional evaluation after ED care.

The goal of this proposal is to evaluate the feasibility of implementing a pragmatic intervention to improve identification of patients at risk for unrecognized cognitive impairment and dementia.

### **2.2 Risks**

This protocol presents minimal risks to participants, as it is an observational, data collection study. The probability and magnitude of harm or discomfort anticipated in the research are no greater than those ordinarily encountered in daily life or during the performance of routine health, memory, and thinking examinations or tests. The primary risks associated with this study are those seen in ordinary life including: responding to health-related interviews, performing health assessments, and sharing health-related information.

### **2.3 Anticipated Benefits**

The potential benefits to study participants include the opportunity for clinical assessments affirming or clearing risk of suspected dementia or related diseases, the coordination and communication about these results with your primary care provider, and receipt of brain health plans if deemed necessary. The benefit to society is the generation of knowledge to improve the care and outcomes of older persons presenting to the ED. As an observational study with no therapeutic intent, the only alternative is for patients to choose not to participate. Therefore, all patients will receive standard clinical care as determined by their physician irrespective of study participation.

### **3 Study Purpose and Objectives**

#### **3.1 Purpose**

This is an observational study of the pragmatic implementation of an ED screening, outpatient referral, and care coordination process for older ED patients who may have UCID. Results from the study will inform plans for a future proposed pragmatic clinical trial. It will evaluate the implementation of an embedded pragmatic, clinical intervention. The intervention will establish a new clinical protocol to assess older adults (age 65+) in the ED for delirium and risk for UCID and refer patients who are found to be at risk for UCID for outpatient evaluation.

#### **3.2 Hypothesis**

We are evaluating the feasibility of implementing a quality improvement initiative of ED screening, referral, and care coordination process of older ED patients with UCID. We hypothesize this will be feasible.

#### **3.3 Objectives**

The primary objective of this pilot project is to evaluate the feasibility of implementing into routine clinical care the assessment for UCID in older ED patients. This will lead to a future multicenter, pragmatic clinical trial proposal.

[figure not shown]
The secondary objective is to determine optimal workflow for integration of cognitive impairment screening, referral assessment, and cognitive health follow-up in a pilot sample of patients and to analyze rates of screening, referral, and diagnosis of UCID.

#### 4 Study Design

This is a multicenter, single-protocol observational pilot pragmatic intervention study that consists of both retrospective and prospective data collection.

The pragmatic intervention that will be evaluated consists of 3-steps: 1. ED assessment for cognitive impairment and outpatient referral, 2. Outpatient assessment and evaluation, and 3. Cognitive Brain Health Planning. For a schematic of the pragmatic intervention, see Figure 1.

Figure 1. Proposed PD4ED Intervention Structure:

#### **4.1 Study Duration**

This study will last for 2 years. The expected duration of subject participation will be approximately 3 months, starting from the date of initial ED evaluation. We anticipate 6 months of subject enrollment and follow-up and then 18 months of data collection, preparation, and analysis.

#### **4.2 Outcome Variables/Endpoints**

As this is a feasibility study, we are not testing hypotheses. Observational results gathered from this study will inform effect sizes needed to propose a future full-scale, pragmatic, multicenter study.

##### **4.2.1 Primary Outcome Variables/Endpoints**

The variables used to assess the primary objective include rates of routine ED screening and detection of delirium, suspected UCID, or no cognitive deficits noted in all older (age 65+ years) ED patients, and rates of successful outpatient referral of patients found to be at risk for UCID.

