##### **4.2.2 Secondary and Exploratory Outcome Variables/Endpoints (if applicable)**

The variables used to assess the secondary objectives include healthcare utilization, rates of outpatient evaluation, confirmation of outpatient assessment, new diagnoses of dementia or mild cognitive impairment (MCI), and changes in outpatient primary care.

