### **5 Study Participants**

#### **5.1 Study Population**

The study will include all ED patients 65+ years in age seen in the YNHH and Northwestern Memorial Hospital EDs that receive an outpatient clinic referral for a cognitive assessment evaluation over January 2021 – December 2021.

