## **8.4 Access to Source**

For identification of eligible participants for recruitment and enrollment, research staff will maintain a password protected screening log to track patients who are referred from the ED

for outpatient cognitive assessment. Participants enrolled will be assigned generated participant identification codes to facilitate the de-identification process.

Data will be collected and merged from clinical and administrative reports and chart review by trained research staff into a single Redcap database.

As this use of administrative and retrospective clinical data and chart review are only minimal risk a waiver of signed consent will be requested.

Source data are all information, original records of clinical findings, observations, or other necessary activities in a research study. Source data are contained in source documents. Research staff at the local site will access the following source documents to extract data for medical record abstraction including: ED records, inpatient records, readmission records, consultations, outpatient records (clinical and office charts), medication administration records and other reports.

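### Screening, detection and referral rates are assigned to a sample of 100 that Section 5.1 limits to referred patients, and referral is secondary in the synopsis but primary in Section 4.2.1

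*Combined protocol and SAP*

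**What the plan says.** **Status of referral.** The synopsis limits the primary outcome to screening and detection: "Primary outcome: ED screening and detection rates of delirium, vs. suspect dementia, vs. no cognitive deficits". Its first secondary outcome is "Rate of screened patients who are referred to outpatient cognitive evaluation". Section 4.2.1 places referral among the primary variables, with a different denominator: "rates of successful outpatient referral of patients found to be at risk for UCID". Section 4.2.2 names "healthcare utilization, rates of outpatient evaluation, confirmation of outpatient assessment, new diagnoses of dementia or mild cognitive impairment (MCI") and changes in primary care, but not ED referral.

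**Source of the rates.** Of the 100 subjects, the synopsis (Number of Participants) says: "These data will provide estimates in rates of screening and referral for a pilot sample of ED patients to ascertain the feasibility". Section 5.2 takes a convenience sample of 100, 50 per site, "to evaluate rate of UCID detection in the ED, rates of referral for outpatient evaluation", along with later outcomes and differences between sites.

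**Who the 100 are.** Section 5.1 defines the study population as ED patients aged 65 or over "that receive an outpatient clinic referral for a cognitive assessment evaluation". Section 8.4, on identifying participants for recruitment, describes a "screening log to track patients who are referred from the ED". Section 5.3 requires only age and discharge from the ED, subject to exclusions, and does not mention referral. Section 6.1.1 describes the 100 as patients eligible for referral.

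**Use of the results.** Section 4.2 says that no hypotheses are tested and that the results will supply effect sizes for a full-scale study. Section 7.1 leaves sample size and power to that later work.

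**The concern.** A rate needs a denominator that includes the patients in whom the event did not happen. If the 100 are all referred, the sample contains nobody who was missed by screening, screened negative, or thought to be at risk but not referred. Those are the patients a feasibility study of screening and referral has to count. The referral rate is then set by selection, and the share of ED patients screened or found at risk cannot be obtained from the sample.

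The change of status adds to this. Referral is primary or secondary, and per at-risk or per screened patient, depending on which page is read. The text that can be read also does not say what makes a referral successful.

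No test result or go/no-go decision is at stake. What is at stake is the pilot's main product: rates on which the later trial can be sized.

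**Working it through.** **1. The plan's own figure.** 2 sites × 50 = 100, which agrees with Section 5.2. The documents give no expected rate, precision target or derivation, so there is nothing further to reproduce.

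**2. What each description of the 100 would yield.** Intervals are exact (Clopper-Pearson) 95%: the lower limit is the 0.025 quantile of Beta(x, n − x + 1) and the upper limit is the 0.975 quantile of Beta(x + 1, n − x). The 60% referral rate, the 10% to 30% at risk and the 250 at-risk patients are assumptions, not document figures.

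- *All referred (Sections 5.1 and 8.4).* Referral = 100/100; per site 50/50; site difference = 0. When x = n the lower limit is 0.025^(1/n): 0.025^(1/100) = 96.4% and 0.025^(1/50) = 92.9%. The narrow intervals reflect selection, not practice. Screening and detection rates cannot be estimated.
- *All at risk, whether or not referred (one reading of Section 6.1.1).* Referral at 60%: 60/100, interval 49.7% to 69.7%; per site 30/50, 45.2% to 73.6%. The referral rate is estimable. Detection is not, because being at risk is then the condition of entry.
- *Any eligible discharged patient (Section 5.3).* With 10% to 30% at risk, 100 × 0.10 = 10 to 100 × 0.30 = 30 at-risk patients. Referral at 60%: 6/10, interval 26.2% to 87.8%; 18/30, interval 40.6% to 77.3%.
- *For comparison, all ED records.* With 250 at-risk patients: 150/250 = 60%, interval 53.6% to 66.1%.

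**3. Whether another section supplies the source.** These sections point to data beyond the 100:

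- Section 4.2.1 sets detection in all older ED patients, but names no data set.
- Section 5.5 seeks a waiver for all older patients' ED records, for comparison with those enrolled.
- Section 6.1.1 plans record review of potentially eligible patients, for clinician compliance and acceptance.
- Section 7 uses all discharged patients aged 65 or over as a denominator, to compare characteristics with referred patients.
- Section 7.2 lists the proportion at risk and the number referred, without a data set or denominator.
- Section 7.3 compares all eligible subjects with the 100.
- Section 9.3 has monthly aggregate ED metrics, for monitoring.

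None assigns the primary rates to the all-patient data, whereas the synopsis and Section 5.2 assign them to the 100.

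**4. How much the referral denominator matters (illustration, all inputs assumed).** Take 1,000 screened patients. Of these, 200 report a memory or thinking problem, 150 of whom the clinician suspects of impairment; a further 100 are suspected without such a report. In each group 60% of those suspected are referred. Suspected = 150 + 100 = 250; referred = 0.60 × 250 = 150.

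- Per suspected patient: 150/250 = 60%.
- Per screened patient: 150/1,000 = 15%.
- Within the memory-problem group: 0.60 × 150 = 90, and 90/200 = 45%.

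**5. How much the meaning of success matters (illustration, assumed steps).** Table 1 collects referral requested, appointment scheduled and appointment completed as separate rows. If 80% of at-risk patients have a referral requested, 70% of those are scheduled and 50% of those are completed, the rate is 80%, 0.80 × 0.70 = 56%, or 0.56 × 0.50 = 28%.

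**The case against.** The strongest reply is that the plan already looks beyond the 100. Section 5.2 opens by saying that all older patients in both EDs will be screened. Section 7.2 does not confine the proportion at risk to the sample, and the two groups in Section 7 would give referred over discharged directly. This stands in part: the data appear to be within reach, so the remedy mostly makes an existing source explicit. It does not remove the conflict, because the only text that names a source for these rates names the 100.

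Three stronger readings are tempting, and the documents do not support them:

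- *A reader might infer that the pilot will report 100% referral and no site difference whatever the practice.* That follows only if the 100 are all referred, which Sections 5.3 and 6.1.1 leave open. Nor does Section 5.2 name a site comparison of referral. It names processes, utilization and outcomes, and placing referral under processes is an inference.
- *A reader might infer that no version of the 100 can give a useful referral rate.* The at-risk reading of Section 6.1.1 gives about 50% to 70% under the assumed rate.
- *A reader might infer that at-risk status has no rule at all, and that clinicians must record a new suspicion item.* Section 6.1 makes clinician suspicion the route to referral, and Table 1 as readable has no row for it. But Figure 1, the intervention schematic, is not shown and may hold a rule. A new prompt could also alter the workflow whose feasibility is being studied.

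It is also fair that no hypothesis, threshold or sample-size derivation depends on these labels. That limits the severity.

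**Conclusion.** The point holds as an unresolved conflict that should be fixed, with medium confidence. Following the synopsis, Section 5.2, Section 5.1 and Section 8.4 together fixes referral at 100/100, makes any site comparison of referral uninformative, and leaves screening and detection without an estimate from the 100. Other sections describe the sample differently, so this is one reading of the plan and not its certain result.

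The contradiction over referral's status and denominator does not depend on that reading. It is direct, and the revision history does not resolve it: its only change after the IRB submission concerns the timing of calls.

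The size and direction of any error cannot be derived from the documents. Every percentage in the working other than the 100/100 and 50/50 results rests on stated assumptions and shows scale only.

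**What to change.** 1. **Source.** Compute screening, detection and referral rates from the record extract of all ED patients aged 65 or over. Extend the purpose given for that records request in Section 5.5 to cover this. Remove these rates from what the 100 are to estimate in the synopsis and Section 5.2. Keep the 100 for interviews and post-referral outcomes.
2. **Sample.** Reconcile Sections 5.1, 5.3 and 6.1.1 on who the 100 are.
3. **Status and denominators.** Give referral one status in the synopsis and in Sections 4.2.1 and 4.2.2. Report it with two labelled denominators: referred over screened, and referred over at-risk patients without documented dementia. Base the at-risk group on data already in Table 1, such as a memory or thinking problem in the prior year, and label it so. Abstract clinician suspicion only where it is already charted, and add no new clinician prompt.
4. **Success.** State which existing Table 1 row counts as a successful referral, and keep it distinct from completed evaluation, which is already a separate secondary outcome.

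The referral rule in Section 6.1 is left as it is. The cost is protocol wording, a slightly wider purpose statement for the records request, some extra analysis, and referral figures that may look less favourable.
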